#### **6.1.6 Safety Evaluation**

Adverse events will be summarized by presenting the proportion of patients having any AE, overall and by body system, and by event as defined by the MedDRA preferred term. Separate summary tables will be provided for IRs, anaphylaxis AEs, and immune complex-related AEs.

For each type of the primary safety endpoints, one event, at most, will be counted per patient. The 95% (exact) confidence interval estimates for each type of safety endpoint will be reported for the rate of incidence at the final analysis. The following hypothesis will be specifically tested: the rate of IRs seen in the Phase 3 studies will be reduced in this study by monitoring SUA prior to infusions and discontinuing therapy if levels increase to above 6 mg/dL, particularly when 2 consecutive levels above 6 mg/dL are observed. With at least 500 patients enrolled with 1 year follow-up, the power of detecting a 26% IR rate (the observed value from the pre-approval Phase 3 studies) against 13% is at least 90%. The rate of IRs reported during the study will be reported and compared descriptively to the rates observed in the pre-approval Phase 3 studies.

Descriptive statistics for laboratory values, vital signs, and their changes from baseline will be provided. Safety data will be listed as appropriate. Further details will be specified in the SAP.

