#### **6.1.2 Background and Demographic Characteristics**

Demographics and other baseline characteristics will be summarized for the ITT population using standard descriptive statistics (number of patients, mean and standard deviation, minimum, median, and maximum), which will be reported and updated for all baseline variables at each data review. All categorical/qualitative data will be presented using absolute and relative frequency counts and percentages. The total number of subjects in the treatment group overall (N) will be used as the denominator for percentage calculations, unless stated otherwise in the SAP. The prediction and profile of the patient's accrual will be made at each review.

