#### **6.1.5 Efficacy Evaluation**

One efficacy endpoint in this study is normalization of SUA to < 6 mg/dL. Descriptive statistics will be employed to summarize the proportion of responders, where a responder is defined as a patient whose SUA values were < 6 mg/dL at their final 2 consecutive study visits. Summary statistics will be provided for the number of swollen joints and tender joints at baseline, 6 months

(Visit 13) and 12 months (Visit 26) or Early Discontinuation; for changes in numbers of gout flares based on patient reported history at 6-week intervals for Months 1-3 and 3-month intervals thereafter; and for elimination of tophi, i.e., the number of patients with a reported tophus resolution at 6 months (Visit 13) and 12 months (Visit 26) or Early Discontinuation.

It is anticipated that there may be a considerable number of study patients who will drop out of the study. The sponsor will make every effort to identify the reason(s) for dropout before reaching the primary safety endpoint. For the analysis of each efficacy endpoint, various sensitivity analyses will be performed under different assumptions of potentially informative dropouts. For example, in the responder analysis, one analysis will be based on the ITT population with various imputation methods for missing values at the end. Analyses will also be performed assuming all “informative” dropouts are non-responders. For continuous efficacy variables, sensitivity analyses will be performed using standard mixed-effect model repeated measure (MMRM) methods. All the analyses will be summarized using 95% confidence interval estimates. The resulting summarized statistics for efficacy will be compared to those reported from the pre-approval Phase 3 studies.

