#### **Safety Population**

The Safety population will consist of all patients who receive at least one (full or partial) infusion of pegloticase. All enrolled patients will be assumed to have taken pegloticase unless otherwise confirmed. If it is confirmed that a patient never took an infusion of pegloticase, then the patient will be excluded from all safety analysis. The safety population will be used for all safety analyses.

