#### **Report Format/Structure**

- Enrollment
  - What has been done to address enrollment over the years?
  - o Number of patients enrolled per calendar year?
  - o Number of sites recruited for study since study initiation
    - Number of actively enrolling sites
      - Number of actively enrolling sites per calendar year
    - Number of sites dropping out per year
    - Reason for site drop outs
- Safety Endpoints
  - O Number of IRs by dose (1st v. 2nd v. 3rd etc.)
  - o IRs by severity or not by dose
  - O Number of anaphylaxis by dose (1st v. 2nd v. 3rd etc.)
  - o Anaphylaxis severity or not by dose
- Efficacy endpoints
  - o Number of patients meeting the primary efficacy effect at 24 and 52 weeks
  - o Number of protocol treated patients meeting the primary efficacy effect
- 1. Patient disposition flow chart:
  - a. Total Number of patients screened
  - b. Number of patients dosed
    - i. Number of patients currently receiving drug
  - c. Number of completers at 24 weeks
    - i. How many were responders versus non responders (based on primary efficacy criteria)
  - d. Number of completers at 52 weeks
    - i. How many were responders versus non responders (based on primary efficacy criteria)
  - e. Number of non-completers at 24 and 52 weeks
    - i. Reason for non-completing (AE, IR, etc.)
  - f. Number of patients treated per protocol through 24 and 52 weeks
    - i. Chart out responders versus non-responders in this cohort
- 2. Dosing:
  - a. Total number of infusions by study cut-off

- b. Total number of infusions per patient
- c. Number of IRs per total number of infusions
- 3. Protocol violations related to time SUA measured before pegloticase infusion
  - a. Number of times SUA was over 6
  - b. Number of patients who continued to receive infusion after SUA > 6 on 2 consecutive occasions in 24 and 52 week cohorts
  - c. Number of patients with premature (> 48 hours before infusion) SUA measures with AE, SAE (IRs, anaphylaxis).
- 4. Protocol violations related to dosing (schedule other than Q2 week dosing)
  - a. Number of patients with dosing violations with AE, SAE (IRs, anaphylaxis).
- 5. Number of patients in follow up
  - a. Reasons for loss to follow-up? (AEs, SAEs, death, etc.)
- 6. How would protocol be amended to encourage enrollment, study compliance, and significantly less number of completers (200) versus the original protocol (500)?

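### The primary safety rates are crude per-patient proportions that count incompletely observed patients as event-free, and drop-out sensitivity analyses are planned for efficacy only

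*Protocol*

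**What the plan says.** Protocol section 6.1.6 sets the counting rule, "For each type of the primary safety endpoints, one event, at most, will be counted per patient", and the interval: "The 95% (exact) confidence interval estimates for each type of safety endpoint will be reported for the rate of incidence at the final analysis". The same section tests whether the IR rate is below the 26% seen in Phase 3.

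On the denominator, protocol section 6.1.2 says "The total number of subjects in the treatment group overall (N) will be used as the denominator for percentage calculations" unless the SAP states otherwise, and the SAP states nothing else for these rates. SAP, Safety Population: "The Safety population will consist of all patients who receive at least one (full or partial) infusion of pegloticase". Protocol section 6.1.1 asks for some follow-up data but sets no length. Neither document gives a censoring rule, a person-time rate, a number at risk or a time-to-event method for the three primary safety endpoints.

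On incomplete observation, protocol section 6.1.5 says "It is anticipated that there may be a considerable number of study patients who will drop out of the study". The remedy it offers covers efficacy: "For the analysis of each efficacy endpoint, various sensitivity analyses will be performed under different assumptions of potentially informative dropouts". For safety it promises only an effort to find out why patients drop out. SAP, Report Format/Structure, reports at a study cut-off and lists "Number of patients currently receiving drug", so partly treated patients are foreseen.

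The SAP also lists IRs per total infusions, and IR and anaphylaxis counts by dose number. Its Tables section adds 24-week-completer tables that include IR and anaphylaxis data. It lists no analysis of immune complex events.

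**The concern.** A proportion with an exact binomial interval estimates a 1-year risk only if every patient is observed for the year or until the event. Two groups break this condition: patients who leave the study while still at risk, and patients part-way through treatment at cut-off. Both stay in the denominator and can add nothing to the numerator after their last contact, so the 1-year risk is understated.

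Stopping the drug is a different matter. An IR needs an infusion, so a patient who has permanently stopped and remains in follow-up is correctly event-free for IRs from then on. The same patient may still develop a delayed immune complex event, and loss from follow-up would hide it.

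These rates are the primary objective. Understatement favours the only hypothesis tested and a reassuring reading of rare immune-mediated events.

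**Working it through.** **1. The plan's own figure.** Section 6.1.6 says "With at least 500 patients enrolled with 1 year follow-up, the power of detecting a 26% IR rate" against 13% is at least 90%. Alpha is not stated; I assume one-sided 0.025, which matches a 95% interval. With n = 500, the exact test against 26% rejects at 110 or fewer patients with an IR (22.0%; attained alpha 0.0220). Power at 13% exceeds 0.9999. The statement holds, but it presupposes one year of follow-up.

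**2. Understatement of the 1-year risk.** The documents give no rate of loss from observation, so this is a range. Assume constant, independent hazards of event (a) and of loss while at risk (b) over one year, with a = −ln(1 − R) and b = −ln(1 − d), where R is the true risk and d the proportion lost.

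Crude proportion = a/(a + b) × [1 − exp(−(a + b))].

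For R = 26% and d = 30%: a = 0.3011, b = 0.3567, sum 0.6578; crude = 0.4577 × 0.4820 = 22.1%.

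| Lost over the year | Crude rate when true risk is 26% | Crude/true for a rare event, d/b |
|---|---|---|
| 10% | 24.7% | 0.95 |
| 20% | 23.4% | 0.90 |
| 30% | 22.1% | 0.84 |
| 50% | 19.1% | 0.72 |

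The last column is the small-a limit (30% loss: 0.30/0.3567 = 0.84) and is the relevant one for immune complex events. It assumes risk spread evenly; if events come late, more are missed.

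**3. The test against 26%.** The placebo-controlled studies lasted 6 months (protocol section 1.2.1), and section 1.2.2 reports IRs in 26% of patients on the two-weekly regimen. Six months here is Visit 13, so I take no reduction to mean a cumulative risk F(13) = 26% by infusion 13. Let a share d leave evenly after infusions 1 to 26 while on drug:

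Crude = (1 − d) × F(26) + d × mean of F(1), …, F(26).

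- *Constant hazard*, F(k) = 1 − 0.74^(k/13): F(26) = 45.2%, mean 25.7%. With d = 1/3, crude = 38.7%. False rejection is about 0.
- *Front-loaded*, F(k) proportional to 1 − exp(−k/6): F(26) = 29.0%, mean 23.2%. With d = 1/3, crude = 27.1%; false rejection 0.6% (n = 500) and 0.2% (n = 1500). The crude rate falls below 26% only when d exceeds (28.98 − 26)/(28.98 − 23.22) = 52%.
- *No risk after infusion 13*, rising evenly to 26% and then flat: mean = 26% × 20/26 = 20%, so crude = 26% − 6% × d. With d = 20%, 24.8% and false rejection 8% at n = 500; with d = 1/3, 24.0% and 16%.

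With up to about half the patients lost, false rejection exceeds 2.5% only if risk is close to nil after month 6.

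**The case against.** A reader might infer that incomplete observation alone would manufacture a reduction against 26%. Setting the 26% at one year seems to show it: with 30% lost, the crude rate is 22.1% and the exact test at n = 500 rejects 51% of the time. The documents do not support that anchor. Under a constant hazard, 26% at one year means 1 − √0.74 = 14.0% at 6 months, already well below the 6-month reference. Anchored at 6 months, the inflation mostly disappears (step 3), because longer observation raises the crude rate. This part of the objection stands.

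A reader might also infer that the test will be run on an immature snapshot. Section 6.1.6 places the interval at the final analysis and section 6.1.7 plans no interim analysis. The synopsis mentions exact intervals at an administrative look, but no test there. The SAP reads largely as a status and feasibility report and specifies no test.

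Loss while on drug is not quantified either. Patients who stop are asked to stay in follow-up (3.5.3, 3.5.6), and those who leave are asked back 4 weeks after the last infusion (3.5.4). That limits the loss but does not remove it, since staying is voluntary.

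The SAP's other summaries help only in part. IRs per infusion and counts by dose number have no at-risk denominators or intervals. Completer tables may omit patients who stopped because of an event. Immune complex events have no listed analysis.

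Finally, the Phase 3 26% is itself reported as a proportion of patients. That justifies keeping the proportion as supportive, but not comparing it over different lengths of observation.

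**Conclusion.** The point holds as a weakness of estimation and should be fixed. The planned proportion understates the 1-year risk whenever patients leave while at risk or are analysed part-way through treatment, and no planned safety analysis shows by how much. Under even, independent hazards, 10% to 30% loss lowers a 26% risk to between 24.7% and 22.1%, and removes about 5% to 16% of a rare risk. These loss rates are assumptions.

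The size and net direction of the effect on the test against 26% cannot be settled from the documents. No loss rate is given, and two influences oppose each other: up to a year of observation against a 6-month reference, and incomplete observation. The power statement is not in error. The clearest gap is immune complex events, where risk can outlast treatment and no analysis is listed.

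**What to change.** In protocol section 6.1.6 and in the SAP:

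- Make the main estimate the cumulative incidence of the first event (Aalen-Johansen, 95% CI, numbers at risk) at Week 25 and Week 51 for each of the three endpoints.
- Treat study exit and data cut-off as censoring. For IR and anaphylaxis, treat permanent drug stop and death as competing events; a temporary interruption is neither, and a reaction to the last infusion counts as the event. For immune complex events, only death competes.
- Use the Week 25 estimate for the comparison with the 6-month 26%.
- Keep the exact proportion as supportive.
- Extend the informative drop-out sensitivity analyses of section 6.1.5 to the three endpoints. Censoring itself assumes that loss is uninformative, so the new estimate does not settle that question alone.

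With complete observation the cumulative incidence equals the crude proportion, so nothing is lost if follow-up is good. The cost is SAP wording and some extra programming on infusion, event and discontinuation data already collected. The stated rates may be slightly less favourable.

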Safety criteria:	IRs, anaphylaxis, and immune complex-related adverse events, serious adverse events and adverse event profile, including gout flares
Statistical methods:	
Descriptive statistics will be employed to summarize the proportion of responders, where a responder is defined as a patient whose SUA values were < 6 mg/dL at their final 2 consecutive study visits. Descriptive statistics will be provided for the number of swollen joints and tender joints at baseline, 6 months and 12 months or Early Discontinuation; for changes in numbers of gout flares based on patient reported history at 6-week intervals for Months 1-3 and 3-month intervals thereafter; and for change in the number of tophi at 6 months (Visit 13) and 12 months (Visit 26) or Early Discontinuation.
 
It is anticipated that there may be a considerable number of study patients who will drop out of the study. The sponsor will make every effort to identify the reason(s) for dropout before reaching the primary safety endpoint. For the analysis of each efficacy endpoint, various sensitivity analyses will be performed under different assumptions of potentially informative dropouts. For continuous efficacy variables, sensitivity analyses will be performed using standard mixed-effect model repeated measure (MMRM) methods. All the analyses will be summarized using 95% confidence interval estimates. The resulting summarized statistics for efficacy will be compared to those reported from the pre-approval phase 3 studies.
 
Adverse events will be summarized by presenting the proportion of patients having any adverse event (AE), overall and by body system, and by event as defined by the Medical Dictionary for Regulatory Activities (MedDRA) preferred term. Separate summary tables will be provided for IRs, anaphylaxis AEs, and immune complex-related AEs.
 
For each type of the primary safety endpoints, one event, at most, will be counted per patient. The 95% (exact) confidence interval estimates for each type of safety endpoint will be reported for the rate of incidence both at the administrative interim analysis, for evaluating the feasibility of the study, and at the final analysis. The following hypothesis will be specifically tested: the rate of IRs seen in the phase 3 studies will be reduced in this study by monitoring SUA prior to infusions and

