discontinuing therapy in patients if levels increase to above 6 mg/dL, particularly when 2 consecutive levels above 6 mg/dL are observed. With at least 500 patients enrolled with 1 year follow-up, the power of detecting a 26% IR rate (the observed value from the pre-approval phase 3 studies) against 13% is at least 90%. The rate of IRs reported during the study will be reported and compared descriptively to the rates observed in the pre-approval phase 3 studies.

There is no planned interim analysis. However, the number of enrolled patients will be reassessed approximately 2 years after the first patient is enrolled. This data will be utilized to make a prediction concerning the future enrollment profile. The enrollment goal may be adjusted depending on the drop-out rate such that approximately 500 patients will complete the 1 year treatment period.

**Assessments:** Baseline samples for identification of antibodies to pegloticase and to PEG, and determination of complement markers (complement component 3 [C3] and complement component 4 [C4]) and tryptase levels. Antibody samples at End-of-Study and at 3-month intervals during follow-up after discontinuation of treatment.

Review of concurrent medications, co-morbidities, and compliance with premedication regimes for gout flares.

Determination of SUA before each infusion.

Recording of drug, dose and timing of IR prophylactic medications.

Recording of infusion start and finish times, sodium chloride diluent used and the total volume infused.

Swollen joint and tender joint counts, and number of tophi to be assessed at baseline, 6 months (Visit 13) and 12 months (Visit 26) or Early Discontinuation.

Flares:

- At baseline, document the history of gout flares from the previous 6 months
- Documentation of the occurrence and duration of any gout flares experienced while the patient is participating in the study

IRs and anaphylaxis:

- Documentation of signs and symptoms and onset time in relation to the initiation of the KRYSTEXXA infusion, and treatment, if any
- Follow-up laboratory assessments may include the collection of samples for analysis of antibodies to pegloticase and PEG, anti-pegloticase IgE, C3, C4, and tryptase levels.

Immune complex disease:

- Clinical investigation of a presumptive immune complex disease (as per clinical practice) and of complement markers (C3, C4) will be pursued.

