### **1.2.1 Efficacy Assessments in Clinical Studies of KRYSTEXXA**

The safety and efficacy of KRYSTEXXA® (pegloticase) has been evaluated in 7 clinical studies, including 2 replicate, multicenter, randomized double-blind, placebo-controlled studies of 6-month duration. In the two placebo-controlled studies, adult patients with chronic gout refractory to conventional therapy were randomized to receive intravenous (i.v.) infusions of KRYSTEXXA 8 mg every 2 weeks or every 4 weeks or placebo in a 2:2:1 ratio. All patients also received prophylaxis for infusion reactions (IRs) and for gout flares. To assess the efficacy of KRYSTEXXA in lowering uric acid, the primary endpoint in both trials was the proportion of patients who achieved plasma uric acid (PUA) less than 6 mg/dL for at least 80% of the time during Month 3 and Month 6. A greater proportion of patients treated with KRYSTEXXA every 2 weeks achieved urate lowering to below 6 mg/dL than patients receiving placebo (38% to 47% of patients receiving KRYSTEXXA vs. 0% of patients receiving placebo). In addition, at Month 6, the percentage of patients who achieved a complete resolution of tophi (defined as 100% resolution of at least 1 target tophus, the appearance of no new tophi, and no single tophus showed progression) was 45%, 26% and 8% with KRYSTEXXA 8 mg every 2 weeks, KRYSTEXXA 8 mg every 4 weeks, and placebo, respectively. Although the 4 week regimen also demonstrated efficacy for the primary endpoint, this regimen was associated with an increased frequency of IRs and was less efficacious with respect to tophi. Therefore, pegloticase 8 mg every 2 weeks was approved by the US FDA on September 14, 2010 for the treatment of adult patients with chronic gout refractory to conventional therapy.

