### **1.2.2 Safety Assessments in Clinical Studies of KRYSTEXXA**

The most commonly reported serious adverse reactions from the pre-marketing controlled clinical trials in patients treated with KRYSTEXXA 8 mg every 2 weeks were gout flare, IR, and anaphylaxis.

Gout flares were more frequent during the first 3 months of treatment (74% in KRYSTEXXA-treated patients vs. 51% in placebo-treated patients), and seemed to decrease over the next 3 months (41% KRYSTEXXA vs. 67% placebo). An increase in gout flares is frequently observed upon initiation of anti-hyperuremic therapy. Thus, all patients in these studies received non-steroidal anti-inflammatory drugs (NSAID) or colchicine or both for at least 7 days as gout flare prophylaxis before beginning KRYSTEXXA; patients continued on this regimen for the 6-month treatment duration.

All patients in Phase 3 clinical trials were pre-treated with an oral antihistamine (fexofenadine, 60 mg by mouth [po], the night before and morning of the infusion), i.v. corticosteroid (200 mg hydrocortisone i.v.) and acetaminophen (1000 mg po) before the infusion to prevent anaphylaxis and IRs. Nevertheless, IRs were reported in 26% of patients treated with KRYSTEXXA 8 mg every 2 weeks compared to 5% of patients treated with placebo. Manifestations of IRs included urticaria, dyspnea, chest discomfort, chest pain, erythema, and pruritus. Approximately 3% of IRs occurred with the first dose, and most (91%) occurred during the infusion rather than after it was completed.

None of the IRs which occurred in the pegloticase studies was categorized as anaphylaxis by the investigators who enrolled subjects in the Phase 2, Phase 3, or open-label extension studies. The US FDA performed a retrospective analysis of the IRs to assess for anaphylaxis, using modified National Institute of Allergy and Infectious Disease/Food Allergy and Anaphylaxis Network (NIAID/FAAN) diagnostic criteria (Sampson et al, 2006). Using their analysis, the frequency of anaphylaxis was 6.5% in all patients treated with KRYSTEXXA 8 mg every 2 week. During randomized, placebo-controlled studies, the frequency was 5% compared to none with placebo. An independent immunologist commissioned by the sponsor to review the data based strictly upon the NIAID/FAAN clinical criteria for anaphylaxis determined the overall rate in the clinical studies to be 2.4%.

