## **3 INVESTIGATIONAL PLAN**

### **3.1 Overall Study Design**

[figure not shown]
This is a Phase 4, multicenter, open-label, single-arm observational study of KRYSTEXXA 8 mg i.v. every 2 weeks in adult hyperuricemic patients with gout refractory to conventional therapy. Approximately 1500 patients will be enrolled in order to observe treatment of up to 500 patients at approximately 300 centers in the United States (US). Study duration is approximately 63 weeks, including 51 weeks of treatment and 12 weeks of follow-up. Patients who discontinue treatment before 51 weeks (i.e., before all 26 planned KRYSTEXXA infusions) will be asked to remain in the study for follow-up assessments for the remainder of their planned treatment duration. It is estimated that approximately 2.5 years will be required for recruitment, from the

first to the last patient's screening visit. The number of patients to be enrolled will be reassessed approximately 2 years after the first patient is enrolled.

Patients not already on a prophylactic regimen of colchicine or NSAID to prevent gout flares should be placed on one of these agents at the time of study entry, unless medically contraindicated (see Section 3.5.7.1). All patients will receive KRYSTEXXA 8 mg i.v. every 2 weeks, admixed in 250 mL of 0.45% or 0.9% Sodium Chloride Injection, USP for i.v. infusion over a target infusion time of 120 minutes. Standardized infusion reaction prophylaxis consisting of pre-treatment with antihistamines and corticosteroids will accompany each infusion (see Section 3.5.8.1). The drug name, dose and timing of these prophylactic medications will be recorded.

A schematic diagram of the study design appears in Figure 1, and the Schedule of Procedures and Evaluations is located in Appendix 3.

**Figure 1** Study Design

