In addition, post-hoc analyses of the clinical study data demonstrated that if KRYSTEXXA had been stopped when a patient's uric acid level rose to greater than 6 mg/dL at 2 consecutive visits, the incidence of IRs would have been reduced by half and there would have been little change in the efficacy outcome. Current guidance for the use of KRYSTEXXA thus recommends monitoring SUA levels prior to infusions and considering discontinuing treatment if SUA levels increase to above 6 mg/dL, particularly when 2 consecutive levels above 6 mg/dL are observed. This study will follow this guidance and provides for the collection of data on both SUA levels and IRs to extend the knowledge base regarding the relationship between these factors.

The design of this study follows the FDA-approved Full Prescribing Information for the use of KRYSTEXXA and allows for capturing additional data related to the safety and efficacy of KRYSTEXXA within the standard healthcare setting. Efforts have been made to limit study-specific activities for the enrolled patients and participating healthcare providers while still allowing for a robust assessment of key safety and efficacy features of KRYSTEXXA treatment in this patient population.

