#### **3.5.8.1 Infusion Reaction Prophylaxis**

Infusion reactions are not uncommon when biological agents are administered by i.v. infusion. Therefore, all patients will receive pre-treatment prophylaxis consisting of at least an antihistamine and corticosteroid prior to each infusion of KRYSTEXXA. In order to standardize this regimen, patients will use 60 mg fexofenadine po the night before and the morning of the infusion and 200 mg hydrocortisone iv before the infusion. If the investigator feels this regimen is not appropriate for an individual patient, s/he should contact the medical monitor to discuss alternative therapy. The name, dose and time of administration of each prophylactic medication will be recorded in the medical record and in the CRF/eCRF.

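### The planned comparison of the IR rate with Phase 3 sets a 1-year proportion against an observed 6-month 26% that it appears to treat as fixed, so the stated power of at least 90% is not assured

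*Protocol*

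**What the plan says.** The synopsis announces a formal hypothesis: "The following hypothesis will be specifically tested: the rate of IRs seen in the phase 3 studies will be reduced in this study", through SUA monitoring and stopping of therapy. The synopsis and section 6.1.6 both give its power for at least 500 patients with 1 year of follow-up: "the power of detecting a 26% IR rate (the observed value from the pre-approval Phase 3 studies) against 13% is at least 90" per cent. At most one event of each type counts per patient, so the endpoint is the proportion with at least one IR.

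The benchmark comes from section 1.2.2: "IRs were reported in 26% of patients treated with KRYSTEXXA 8 mg every 2 weeks compared to 5% of patients treated with placebo". Section 1.2.1 describes the placebo-controlled trials as "2 replicate, multicenter, randomized double-blind, placebo-controlled studies of 6-month duration". The 13% is half of 26% and matches section 3.2, where a post-hoc analysis of the earlier data found that, had treatment stopped after two consecutive high uric acid values, "the incidence of IRs would have been reduced by half".

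Neither document gives the Phase 3 denominator, a test, an alpha level or a sidedness. The same paragraph of 6.1.6 goes on to call the Phase 3 comparison descriptive, and section 6.2 says that no formal sample size calculation was made. Section 6.1.6 leaves further details to the SAP. The SAP assigns safety analyses to the Safety population (everyone with at least one full or partial infusion) and lists IRs by dose, by severity and per infusion, plus tables for 24-week completers. It contains no comparison with Phase 3.

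**The concern.** Two features of the comparison pull in different directions.

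**Window.** For a fixed group of patients, the proportion who have ever had an IR can only stay level or rise between month 6 and month 12. Setting a 1-year proportion against a 6-month benchmark can therefore hide a real reduction. It cannot create one.

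**Benchmark.** The 26% is itself an estimate. The power statement uses only this study's sample size, so it appears to treat 26% as exact. If the test were run that way, a Phase 3 figure that was high by chance could make an unchanged rate look reduced.

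This is the only hypothesis stated for the primary safety objective. A 1-year rate far below 26% would still be informative. Moderate differences are the difficulty, because the plan gives no rule for reading them and the quoted power covers neither feature.

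**Working it through.** **Inputs from the documents:** benchmark 26% over 6 months; alternative 13%; n = 500; at most one event per patient.

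**Assumptions, not in the documents:** one-sided alpha 0.025; Phase 3 arm size N0 = 50, 100, 200 or 400; k, the hazard of a first IR in months 7-12 relative to months 1-6.

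**1. The plan's own figure.** Exact binomial test of p = 0.26, n = 500. The rule is to reject if 110 or fewer patients have an IR, because P(X ≤ 110 | 0.26) = 0.0220. Power is P(X ≤ 110 | 0.13) > 0.9999. The stated lower bound of 90% is met if 26% is fixed and 13% is the 1-year rate.

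**2. Window, with 26% still fixed.** Let 13% be the 6-month risk. The 1-year risk is 1 − 0.87^(1+k), and power is P(X ≤ 110) at that risk.

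| k | 1-year risk | Power, n = 500 |
|---|---|---|
| 0 | 13.0% | >99.9% |
| 50% | 18.9% | 97% |
| 75% | 21.6% | 60% |
| 100% | 24.3% | 12% |

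Power passes below 90% at k of about 58%.

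**3. Benchmark, in the test as apparently planned.** Suppose the true 6-month rate is 26% in both studies. The 1-year rate here is then 1 − 0.74^(1+k), that is 26.0%, 30.3% and 33.0% at k = 0, 20% and 33%. Draw the Phase 3 count X0 from Bin(N0, 0.26), treat X0/N0 as fixed, and find the critical value c(X0) at 0.025. The chance of a false claim of reduction is the sum over X0 of P(X0) × P(X ≤ c(X0)).

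| N0 | k = 0 | k = 20% | k = 33% |
|---|---|---|---|
| 50 | 26% | 10% | 4.6% |
| 100 | 20% | 4% | 1.2% |
| 200 | 14% | 1% | 0.2% |
| 400 | 9% | 0.3% | <0.1% |

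The nominal rate is 2.5%. Late first IRs reduce the error quickly, so the two problems partly offset each other.

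**4. Windows matched, Phase 3 error carried.** Once both proportions are at 6 months, that offset is gone and the comparison has to be two-sample. With SE1 = √(0.26×0.74/N0 + 0.13×0.87/500), the unpooled z-test has power Φ(0.13/SE1 − 1.96). The pooled version is Φ((0.13 − 1.96×SE0)/SE1), where SE0 = √(p̄(1 − p̄)(1/N0 + 1/500)) and p̄ is the weighted mean rate.

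Example, N0 = 100:
- SE1 = √(0.001924 + 0.000226) = 0.0464. Unpooled power is Φ(2.80 − 1.96) = 80%.
- p̄ = (26 + 65)/600 = 0.152 and SE0 = 0.0393. Pooled power is Φ((0.13 − 0.0770)/0.0464) = 87%.

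| N0 | Power (unpooled to pooled) |
|---|---|
| 50 | 53-67% |
| 100 | 80-87% |
| 200 | 96-98% |
| 400 | 99.8% |

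Power of 90% needs N0 of about 113 (pooled) to 140 (unpooled).

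**The case against.** The strongest reply has four parts.

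*The power figure is correct.* That stands: step 1 reproduces it with room to spare, so a reader should not infer that the study is too small on its own terms. Nor do the documents support saying that the 90% holds only under a fixed 26% and a 1-year 13%. It also holds at k = 50% against a fixed 26%, and at N0 = 200 with the benchmark error carried.

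*Nothing says that 26% is fixed.* Also fair. The protocol never calls the test one-sample, and a Phase 3 arm of about 113-140 or more would support the claim on a two-sample reading with matched windows. The fixed benchmark is inferred from the absence of any Phase 3 denominator or variance.

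*The false-claim rates are a corner case.* Largely right. The 9-26% figures need equal true rates and no first IR after month 6. At k = 33% only N0 = 50 stays above 2.5%. A reader might take 26% as the false-positive rate of the plan; the documents do not support that.

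*The objective is descriptive and the intervals serve it.* The planned exact 95% interval is for this study's own rate and is sound. No interval for a difference is planned, so none can be called too narrow. But a purely descriptive aim does not fit with a named hypothesis and a power claim in the same paragraph.

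The SAP's 24-week tables do not close the gap, since they cover completers only and are not tied to the hypothesis. The 200 patients that the SAP asks about are likewise completers of 24 weeks' treatment. That number cannot stand in for the Safety population, given "Approximately 1500 patients will be enrolled in order to observe treatment of up to 500 patients".

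**Conclusion.** The point holds and should be fixed, but it is not fatal. The comparison mixes a 1-year and a 6-month proportion, names no test, alpha or sidedness, and is called both a test and a description. The stated power is a valid lower bound on its apparent terms but is not assured outside them. At n = 500 it drops to 60% at k = 75% and 12% at k = 100% if 13% is a 6-month risk. On a matched window with Phase 3 error carried, it is below 90% for a Phase 3 arm smaller than about 113-140.

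The window error is conservative. The benchmark error can favour a false claim of reduction, but mainly when few first IRs occur late. All these sizes rest on N0, k and one-sided 0.025, which the documents do not give. Confidence is high on the window mismatch and medium on the fixed benchmark.

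**What to change.** In section 6.1.6, the synopsis and the SAP:

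1. Compare first-IR incidence through 6 months in the SAP's Safety population with the Phase 3 numerator and denominator. Name a two-sample test (for example Fisher's exact test), its alpha and its sidedness, and give a 95% interval for the difference that carries both variances.
2. Report 12-month incidence separately with its exact 95% interval.
3. Restate the power on that basis and reconcile it with section 6.2. If the comparison is meant to be descriptive only, delete the test and the power claim.
4. State that the comparison is historical and single-arm, so that a lower rate is not by itself attributable to SUA monitoring. Premedication is one example of a possible difference: section 1.2.2 lists acetaminophen in Phase 3, while section 3.5.8.1 asks for "pre-treatment prophylaxis consisting of at least an antihistamine and corticosteroid prior to each infusion", which neither requires nor excludes it.

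The cost is wording, plus Phase 3 counts that the sponsor should hold; infusion times and adverse event dates are already collected. The downside is a wider interval and possibly a lower stated power. For 26% against 13% at n = 500, the half-width 1.96 × SE1 is 12.5, 9.1, 6.8 or 5.2 percentage points at N0 = 50, 100, 200 or 400.
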